3.2.2.2 Abilify MyCite System Onboarding

Onboarding involves the pairing of a patch with the application contained on a smartphone and then applying that patch to the skin in the proper location.

During the Abilify MyCite onboarding process, the smartphone app will provide guidance for skin preparation and patch placement. A simple skin preparation procedure, consisting of gently cleaning the skin surface and allowing the area to dry, is recommended. On some subjects, clipping of body hair in the placement zone may be required to allow secure device adhesion. Placement of the patch should avoid locations below the bottom of the rib cage or areas where the patch was previously worn. Use of lotions on the skin where the patch will be placed is not recommended. The patch can be worn during regular activities including showering, but new patches should not be applied for a few hours after showering or other physical activities to ensure the adhesive sticks properly. The smartphone app will remind subjects when the patch needs to be changed.

3.2.2.3 Abilify MyCite System Patch Use

Throughout the assessment period, the subject will be notified by the smartphone app when the patch needs to be changed. No patch should remain applied to a subject's skin for longer than the intended patch duration.

Following the initial patch pairing and placement during the baseline visit, a subject will be instructed to wear a patch continuously (eg, 24 hours per day, 7 days per week), if possible. The patch can be worn throughout different daily activities, including bathing and swimming.

Protocol 031-201-00301

A subject will be told that it is allowable to remove the patch for any reason (especially for evidence of local skin irritation/inflammation), but that it is preferred that the patch be kept on as much as is tolerable and safe. The subject should note, as much as possible, the events surrounding any premature removal of the patch and contact the site immediately. A reason must be recorded for every patch removal, including reasons for premature patch removal, in the eCRF. Subjects are free to replace a patch offsite using dispensed trial supplies.

Each subject will return all supplies, including all used patches and associated labels, to the trial site. At the end of the trial (Month 6/ET visit), all returned patches and associated labels will be destroyed at the trial site(s) or by a designated agent.

3.3 Trial Population

The trial population will include male and female subjects, 18 to 65 years of age, inclusive, with a diagnosis of schizophrenia according to DSM-5 criteria. Subjects must have had at least 1 inpatient psychiatric hospitalization within 4 years (48 months) prior to screening. Subjects must have been prescribed oral antipsychotic treatment for at least 6 months or longer prior to screening. Approximately 493 subjects will be screened in order to enroll 320 subjects and complete 224 subjects.

3.3.1 Number of Subjects and Description of Population

3.3.2 Subject Selection and Numbering

All subjects will be given a unique 5-digit subject identification number after signing the informed consent form (ICF).

3.4 Eligibility Criteria

3.4.1 Informed Consent

Informed consent will be freely obtained from all subjects (or their guardian or legally acceptable representative, as applicable for local laws). The ICF will be approved by the same Institutional Review Board (IRB) that approves this protocol. Additionally, the informed consent will cover the retrospective, screening, and prospective aspects of the trial.

Each ICF will comply with the International Council for Harmonisation (ICH) Good Clinical Practice (GCP) Guideline and local regulatory requirements. The investigator will ensure that the sponsor reviews and authorizes any site-specific ICF used in the trial before submission to the IRB.

Protocol 031-201-00301

The investigators may discuss trial availability and the possibility for entry with a potential subject without first obtaining consent. However, informed consent must be obtained and documented prior to initiation of any procedures that are performed solely for the purpose of determining eligibility for research, including withdrawal from current medication(s).

Potential subjects are free to refuse entry into the trial, or withdraw from the trial at any time, without justification, and there will be no consequences to their further care.

Prospective trial participants will be provided with controlled access to the electronic ICF (eICF) application by trial site staff. When the trial site staff and the participant agree that the participant has enough information to make an informed decision to participate, the participant will electronically sign in the eICF application and an electronic date and timestamp will be applied to the signature. The subject will be given a printed, signed copy of the ICF. Any other parties required by the IRB (trial site staff, witnesses, or legally authorized representative) are also required to sign electronically and these signatures will be stored with the eICF in accordance with the ICH GCP guideline and local regulatory requirements/guidelines. These signatures cannot be altered, removed, or copied.

Subjects may be asked to sign additional ICFs if the protocol is amended and the changes to the protocol result in additional information that needs to be provided to the subjects, so that they can make a knowledgeable and voluntary decision on trial participation.

Eligible participants include adult subjects with a current diagnosis of schizophrenia being treated with aripiprazole, or for whom aripiprazole treatment would be appropriate, as determined by the treating physician. Subjects must also meet all of the inclusion criteria ([Section 3.4.2](#)) and none of the exclusion criteria ([Section 3.4.3](#)).

3.4.2 Inclusion Criteria

Subjects are required to meet the inclusion criteria presented in [Table 3.4.2-1](#).

1.	Subject must be willing and able to give written (signed and dated) informed consent, which includes adherence to trial requirements and restrictions before enrolling in the trial. Subject must be willing to adhere to trial procedures, including troubleshooting of the Abilify MyCite app by a third party if needed.
2.	Subject must be able to read and understand English.
3.	Male and female subjects 18 to 65 years of age, inclusive, at the time of informed consent.
4.	Subjects are deemed appropriate, per investigator judgment, to use Abilify MyCite and to enter this interventional trial.

Protocol 031-201-00301

Table 3.4.2-1 Inclusion Criteria	
5.	Subject must possess a smartphone and is familiar with its use and is willing to download and interact with the Abilify MyCite app, completing all tasks as well as adequately operating all devices, as applicable. Caregiver/support person or other third party assistance can be utilized throughout participation in the trial. However, subjects should be encouraged to complete all tasks themselves. At the conclusion of the study, the caregiver/support person will be asked (where applicable) to provide feedback via the Caregiver Involvement Scale. A subject with a smartphone that is not compatible with the Abilify MyCite app will be offered a loaner phone for the trial period.
6.	Subject possesses the capacity to utilize the technology interfaces (eg, open and navigate software applications using the touch screen) and telephone features of a smartphone (Android or iOS). The subject has satisfactory mobile phone reception (preferably 3 bars or more or have Wi-Fi) at home and/or at work for wireless carrier.
7.	Subject is cooperative, able to ingest oral medication, willing to complete all aspects of trial, and capable of reporting AEs.
8.	Clinical diagnosis of schizophrenia (defined by DSM-5) with a PANSS total score between 60-90.
9.	Subjects currently prescribed oral atypical antipsychotic medication including aripiprazole or appropriate for aripiprazole treatment for 6 months or longer.
10.	Subjects are required to have had an inpatient hospitalization for schizophrenia within the last 48 months prior to entering the trial.
11.	Subject's general medical condition such that participation in the trial does not pose any additional risk as per investigator's judgment.
12.	Skin on the anterior chest just above the lower edge of the rib cage that is free of any dermatological problems (eg, dermatosis or dermatitis, open wounds, or other skin disorders such as warts, rashes, atopic dermatitis, or irritations).

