7.1 Sample Size

The primary endpoint of this trial compares the paired proportions of inpatient psychiatric hospitalization during the retrospective period (Month 1 to 3) and the prospective period (Month 1 to 3), which will be analyzed using a McNemar test.

Based on published results of other similar studies for the particular time periods (retrospective Month 1 to 3 and prospective Month 1 to 3)^{23,24} we are evaluating, it is reasonable to assume that 15.5% of subjects are hospitalized during retrospective Month 1 to 3 and 7% are hospitalized during prospective Month 1 to 3; about 5% of subjects who are not hospitalized retrospective will be hospitalized prospective, while 13.5% of subjects who are hospitalized retrospective will not be hospitalized. With this assumption, 200 completed subjects will provide 80% power (alpha = 0.05 two-sided) to detect a difference of 8.5% in 2 paired hospitalization proportions between pre-switch and post-switch periods while the proportion of total discordant pairs is 18.5%. In addition, this sample size will provide 80% power for the comparison of retrospective Month 4 to 6 vs prospective Month 4 to 6, assuming 30% of the subjects are hospitalized pre-switch (12.5% subjects will be hospitalized post-switch and another 17.5% won't have hospitalization post-switch) and, overall, 20% are hospitalized post-switch (among them, 12.5% subjects are hospitalized both pre-switch and post-switch and 7.5% have no hospitalization pre-switch).

Two interim analyses are planned at when 50% and 70% of subjects have completed the prospective period (Month 1 to 3); in order to conserve the overall Type I error at 0.05 level, 224 to 300 evaluable subjects are needed to complete the 3-month treatment to maintain 80% power. This sample size assumes the 3 sequential tests are made using LanDeMets Spending Function²⁵ with O'Brien-Fleming boundary, a futility conditional power of 15% is built in the sample size calculation to allow the trial to stop for futility. Based on the conditional power and the alpha level at the interim analysis, the trial could stop for efficacy or futility, continue with initially planned 224 sample size or increase to up to 300 if the conditional power fall between 30% to 80% (Section 7.4.4). The 2-sided alpha levels for these 2 interim analyses are 0.00312 and 0.0139 respectively, and the alpha left for the final analysis will be 0.04528.

Protocol 031-201-00301

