7.4.1 Primary Endpoint Analysis

The primary endpoint of this trial is the comparison of inpatient psychiatric hospitalization rates (proportion of subjects with ≥ 1 inpatient psychiatric hospitalization[s]) between the retrospective period (Months 1 to 3) while on oral standard-of-care antipsychotic treatment and the prospective period (Months 1 to 3) after the switch to Abilify MyCite. This will be achieved by testing for statistically significant (at 2-sided overall alpha = 0.05). The analysis will be performed using a McNemar test on those who have hospitalization data during Months 1 to 3 prior to the screening period and during Months 1 to 3 after switch to Abilify MyCite.

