7.1.2 Technical Details

Inpatient psychiatric hospitalization is defined as closed (locked) ward or open ward inpatient psychiatric hospitalization, where the hospitalization is not primarily for psychosocial reasons.

The start date and end date of the retrospective period Months 1-3 are calculated in the following ways: start date = (Date signing informed consent - 28*6 Days) and end date = (Date of signing informed consent - 28*3-1 Days). The start date and end date of the prospective period Months are calculated as: start date = (Mycite start date) and end date = (Mycite start date + 28*3 - 1). Similarly, the start date and end date of the retrospective period Months 4-6 are calculated in the following ways: start date = (Date signing informed consent - 28*3 Days) and end date = (Date of signing informed consent -1 Days). The start date and end date of the prospective period Months are calculated as: start date = (Mycite start date + 28*3) and end date = (Mycite start date + 28*6 - 1).

Inpatient psychiatric hospitalization is deemed to occur during the retrospective (or prospective) Months 1-3 if:

- The hospitalization starts before the start date of retrospective (or prospective) Months 1-3 and continues into Months 1-3
- The hospitalization starts during the retrospective (or prospective) period.

Similarly, Inpatient psychiatric hospitalization is deemed to occur during the retrospective (or prospective) Months 4-6 if:

- The hospitalization starts before the start date of retrospective (or prospective) Months 4-6 and continues into Months 4-6
- The hospitalization starts during the retrospective (or prospective) period

All the above hospitalization in Months 1-3 and Months 4-6 will be counted in the Month 1-6 period.

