7.1.3 Sensitivity Analyses

As sensitivity analysis, the primary efficacy analysis will be performed on the mITT subjects who have completed the 3-month treatment only that is all subjects who are in study for at least 75 days (12 weeks adjusting for the 9 days allowed for visit window).

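### The 48-month admission criterion selects on the retrospective window but not on the prospective one, so the primary comparison leans towards MyCite under no effect, by an amount that depends on an admission rate the documents do not give

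*Protocol*

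**What the plan says.** Criterion 10 in Protocol 3.4.2 reads: "Subjects are required to have had an inpatient hospitalization for schizophrenia within the last 48 months prior to entering the trial". Protocol 3.3 repeats the 48-month requirement, there for any inpatient psychiatric admission before screening.

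SAP 7.1.2 sets the retrospective Months 1-3 as "start date = (Date signing informed consent - 28*6 Days) and end date = (Date of signing informed consent - 28*3-1 Days", which is days -168 to -85 (84 days). The prospective Months 1-3 are "start date = (Mycite start date) and end date = (Mycite start date + 28*3 - 1", also 84 days.

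The only primary comparison is between these two windows in the same subjects, with no control group. Protocol 7.4.1 describes "testing for statistically significant (at 2-sided overall alpha = 0.05" and adds: "The analysis will be performed using a McNemar test on those who have hospitalization data during Months 1 to 3 prior to the screening period". Protocol 7.1 assumes that "15.5% of subjects are hospitalized during retrospective Month 1 to 3 and 7% are hospitalized during prospective Month 1 to 3".

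Protocol 3.6, on bias, says only that the trial is open-label. In SAP 7.1.3 the sensitivity analysis is that "the primary efficacy analysis will be performed on the mITT subjects who have completed the 3-month treatment only". SAP Appendix 2 also lists the primary table for the ITT sample (CT-5.1.2).

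**The concern.** An admission in the retrospective window can itself satisfy criterion 10. An admission in the prospective window cannot. The sample is thus chosen on having had an event in a span that contains one of the two compared windows and not the other. McNemar's null of equal paired proportions then fails with no treatment effect, and a larger sample makes rejection more likely. The plan allows an increase to 300.

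At stake is the meaning of a significant primary result. Some of the fall would come from eligibility, and the same test drives efficacy stopping at both interims. The completer analysis and the ITT table do not help. SAP 5.1.1 requires ITT subjects to meet the inclusion criteria, and mITT is a subset of ITT, so both carry the same selection.

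**Working it through.** **The plan's own figure.** Inputs from Protocol 7.1: discordant cells 13.5% and 5%, so pd = 0.185 and d = 0.085.

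n = [1.960·√pd + 0.842·√(pd − d²)]² / d² = 198.6, or 199 against the stated 200. The sample size reproduces.

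**Direction.** Let E be at least one admission in the 48 months, A an admission in the retrospective window and B one in the prospective window. Assume no drug effect and a constant admission rate for each subject, so P(A) = P(B). Because A implies E:

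- P(A|E) = P(A)/P(E)
- P(B|E) = [P(B) − P(B and not E)]/P(E)
- gap = P(B and not E)/P(E), which is never negative

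**Upper limit.** Let L(t) be the probability of no admission in t days, and take 48 months as 1461 days. The gap is [L(1461) − L(1545)]/[1 − L(1461)]. L is decreasing and convex for any mixture of constant rates, so the gap cannot exceed 84/1461 = 5.75 points.

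**Constant rate, no-effect prospective rate 7%.** The rate per 84 days is −ln(0.93) = 0.0726, and 1461/84 = 17.39.

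- P(not E) = exp(−0.0726 × 17.39) = 0.283, so P(E) = 0.717
- retrospective rate = 0.07/0.717 = 9.76%
- gap = 0.07 × 0.283/0.717 = 2.76 points

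**Constant rate, enrolled retrospective rate 15.5%.** Solving gives a rate of 0.1564 per 84 days and P(E) = 0.934.

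- retrospective rate = 0.1448/0.934 = 15.5%
- prospective rate = 14.48%
- gap = 1.02 points

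**Between-subject variation.** With gamma frailty of shape k and mean m per 84 days, L(t) = (1 + mt/(84k))^(−k). The proportion admitted in both windows is [1 − 2L(84) + L(168)]/P(E), which gives the discordant cells p10 (retrospective only) and p01 (prospective only). Two-sided rejection of the asymptotic McNemar test at 0.05, by exact enumeration:

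| Anchor | Frailty | Retro | Prosp | Gap (points) | p10 / p01 | 224 pairs | 300 pairs |
|---|---|---|---|---|---|---|---|
| Retro 15.5% | none | 15.5% | 14.5% | 1.0 | 13.3% / 12.2% | 6.0% | 6.5% |
| Retro 15.5% | k = 0.5 | 15.5% | 13.4% | 2.1 | 12.4% / 10.3% | 9.8% | 11.6% |
| Prosp 7% | none | 9.8% | 7.0% | 2.8 | 9.1% / 6.3% | 18.3% | 22.8% |
| Prosp 7% | k = 0.5 | 10.2% | 7.0% | 3.2 | 9.2% / 6.1% | 22.6% | 28.5% |

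**Planned boundaries.** I simulated looks at 112, 157 and 224 with the stated alphas (0.00312, 0.0139, 0.04528) and futility below 15% conditional power under the current trend, without the increase to 300. Rejection is about 4% to 8% at the 15.5% anchor and about 15% to 19% at the 7% anchor. With equal discordant cells (9.25% each) the same design rejects about 2.2% of the time, because futility removes most results against MyCite.

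**Check of the proposed subset.** Select instead on an admission between 48 months and 168 days before consent. Both windows then fall after the selecting span and have equal length, so under a constant rate the two proportions agree. Simulation at the 7% anchor gave 7.0% to 7.2% against 7.0% to 7.1%, with rejection in 5.0% to 5.6%.

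**The case against.** The strongest counter-argument concerns size. A reader might infer that false positives are far above 5% whatever the rate. The documents do not support that. The 7% in Protocol 7.1 is the expected rate after the switch, with the hoped-for benefit already in it. The plan's only figure for standard of care is 15.5%, and there the inflation is modest. This stands, and it is why the result must be given as a conditional range. It does not make the low-rate case remote. Under the model, a 15.5% retrospective rate implies about 2.9 to 3.1 admissions per subject in the 48 months and the 7% case about 1.8 to 1.9, while criterion 10 asks for one. The 15.5% is borrowed from other studies.

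The single-test figures also are not those of the planned design. That stands too: the boundaries with futility lower them somewhat.

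The overlap is not exact. Criterion 10 needs an admission for schizophrenia, while the endpoint counts any inpatient psychiatric stay that is not primarily psychosocial, including stays already in progress when the window opens. The model ignores this; the effect is probably small.

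Finally, the proposed subset is balanced only under a constant rate. If risk declines after an admission, the retrospective window is still nearer the qualifying event. In one illustrative simulation (hazard raised fourfold after admission, decaying over 180 days) the subset still showed 7.2% against 6.6%. The fix must carry that qualification.

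**Conclusion.** The concern holds in a conditional form. Criterion 10 biases the primary comparison towards MyCite, and no listed analysis removes the bias. For a single two-sided 0.05 test at 224 pairs:

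- **Enrolled retrospective rate 15.5%:** spurious fall about 1 to 2 points (12% to 24% of the planned 8.5), false positives about 6% to 10%.
- **No-effect rate 7%:** fall about 2.8 to 3.2 points (about a third of the planned effect), false positives about 18% to 23%, and about 23% to 28% at 300 pairs.

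These figures assume no drug effect, a constant admission rate per subject, frailty from none to gamma shape 0.5, 48 months taken as 1461 days, and length of stay ignored. The documents give neither a no-effect rate nor the distribution of time since the qualifying admission, so they cannot settle which case applies.

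A reader might also infer that eligibility alone could generate the planned result. It could not, since 5.75 points is the ceiling under this model.

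Severity: should be fixed. The bias affects the only primary test, but it is modest at the plan's own pre-switch rate and can be examined without changing eligibility or the test.

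**What to change.** At screening, record the date of the latest inpatient admission for schizophrenia (as criterion 10 defines it) before consent minus 168 days.

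In SAP 7.1.3, prespecify the primary McNemar test and the paired difference in subjects with such an admission between 48 months and 168 days before consent, whether or not they were also admitted in the retrospective phase. Report this beside the primary result and limit the efficacy conclusion to what both support.

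State in the SAP that this removes the selection from criterion 10 under a constant admission rate. State also what it leaves in place: declining risk after an admission, withdrawal of subjects who need hospitalisation during tolerability assessment or cross-titration (Protocol 3.2.1), and the requirement of at least 80% of study medication for mITT (SAP 5.1.1).

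Cost: one date field, which sites can take from the records used to confirm criterion 10, and one table. About 2% to 7% of subjects, those whose only qualifying admission falls in the last 168 days, are left out of that analysis. For example, at a constant rate and 7%: exp(−0.0726 × 1293/84) × [1 − exp(−0.0726 × 2)]/0.717 = 6.2%.

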3.4.3 Exclusion Criteria

Subjects will be excluded if they meet any of the exclusion criteria in [Table 3.4.3-1](#).

Table 3.4.3-1 Exclusion Criteria	
1.	Females who are breast-feeding and/or who are pregnant at the time of trial enrollment, or who plan to become pregnant during the trial.
2.	Sexually active males or WOCBP who do not agree to practice 2 different methods of birth control or remain abstinent during the trial and for 30 days after the last dose of Abilify MyCite. If employing birth control, 2 of the following precautions must be used: vasectomy, tubal ligation, vaginal diaphragm, intrauterine device, birth control pill, birth control implant, birth control depot injection, condom with spermicide, or sponge with spermicide.
3.	Any subject who participated in another clinical trial within 30 days of enrollment into the current trial.
4.	Subjects who are currently being treated with an LAI antipsychotic or have been treated with an LAI in the retrospective 6-month phase.
5.	Subjects with a current DSM-5 diagnosis other than schizophrenia, including schizoaffective disorder, bipolar I disorder, MDD, delirium, dementia, amnesic, or other cognitive disorders. Also, subjects with borderline, paranoid, histrionic, or antisocial personality disorder.
6.	Subject with any disorder including but not limited to intellectual developmental delay or disorder, major neurocognitive disorder or other condition that may impact the subject's ability to participate in the trial or interact with the smartphone application.
7.	Subject who is likely to be incapable of using the Abilify MyCite technology, even with assistance.

Protocol 031-201-00301

Table 3.4.3-1 Exclusion Criteria	
8.	Subject who has a history or evidence of a medical condition that would expose them to an undue risk of a significant AE or interfere with assessments of safety or usability during the course of the trial, including but not limited to, hepatic, renal, respiratory, cardiovascular, endocrine, neurologic, hematologic, or immunologic disease as determined by the clinical judgment of the investigator.
9.	Subject with a known allergy to adhesive tape or any pertinent components of the patch or aripiprazole tablet embedded with an IEM sensor (Abilify MyCite).
10.	Any subject who, in the opinion of the investigator or the medical monitor, should not participate in the trial.

LAI = long-acting injectable; WOCBP = women of childbearing potential.

Nonchildbearing potential is defined as male and female subjects who are surgically sterile (ie, male subjects who have undergone bilateral orchidectomy and female subjects who have undergone bilateral oophorectomy and/or hysterectomy) and female subjects who have been postmenopausal for at least 12 consecutive months.

Subjects must agree to restrictions to medications as described in [Section 4](#).

